6.7. Electrocardiogram (ECG)

The Electrocardiogram (ECG) assessment will measure PR Interval (msec), QRS Duration (msec), QT Interval (msec), QTcF Interval (msec), QTcB Interval (msec), Heart Rate (bpm), and RR Interval (msec). The assessment will be done at the Screening visit (Visit 1), Baseline (Visit 3), Visit 5 (Week 2), Visit 9 (Week 6), End of Treatment (Week 13, Visit 16) and Follow-Up (Visit 17). The interpretation of the results will be assessed as Normal or Abnormal, and any Abnormal results will be assessed for clinical significance. The subject should be supine for at least 5 minutes before the first ECG is taken. If this cannot be done, this will be documented in the CRF. The ECG will be obtained as a continuous ECG of at least 50 ms. All readable ECGs of at least 10 ms will be interpreted by the central reader and reported.

Summary statistics for each ECG parameter and the change from baseline will be presented at each post-baseline visit. Additionally, summary statistics for the shifts in interpretation from baseline will be presented at each post-baseline visit. All ECG measurements will be presented in data listings.

6.8. Prior and Concomitant Medications

Prior and concomitant medication verbatim terms captured via the EDC system will be mapped to Anatomical/Therapeutic/Chemical (ATC) class and Preferred Names using the September 1, 2022 version of the World Health Organization (WHO) Drug Dictionary Enhanced available.

Prior and concomitant medications will be summarized separately by WHO ATC class and preferred name. Medications with an end date prior to first dose will be considered prior medications. Medications that are taken during while on study medication will be considered concomitant medications. These summaries will present the number and percent of subjects using each medication. Subjects may have more than one medication per ATC class and preferred name. At each level of subject summarization, a subject is counted once if one or more medications at that level is reported for the subject. Each summary will be ordered by descending order of incidence of ATC class and preferred term.

6.9. Total, Monthly, and Weekly Seizure Episodes

Evaluation of total, monthly, and weekly seizure frequency will be derived as defined in Section 4.3. Seizure frequency will be assessed from a seizure diary that is part of the Caregiver Diary which is completed daily by the caregiver.

Summary statistics on the observed and the change from baseline in total and monthly seizures will be displayed at baseline and end of treatment. Within subject changes will be assessed using a Wilcoxon Signed Rank Test.

7. Efficacy Analysis

The secondary objective of the study is to investigate measures of efficacy during treatment with NNZ-2591 in children and adolescents with PMS.

All efficacy analyses will be conducted on the ITT population.

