4.3. Definitions

- The baseline measurement for an efficacy variable will be based on the average values of visits 1-3 for assessments collected at more than one visit. For assessments collected once during the Screening/Baseline period, the most recent non-missing assessment will be used. For safety assessments, value at Visit 3 (Baseline) or the most recent non-missing assessment will be used.
- Age will be derived as the integer value of informed consent/assent date minus birth date plus one, then divided by 365.25.
- The age at time of assessment in calculated as (date of assessment date of birth + 1)/365.25.
- Body Mass Index (BMI) will be derived as weight in kilograms divided by height in meters squared.
- The change from baseline measurement for a variable at a particular visit will be derived as the measurement taken at the specified visit minus the baseline measurement. CGI-I will not have a change from baseline measurement; the within-subject treatment change is assessed by the value at the End of Treatment Visit.
- Treatment duration in days will be derived as follows: Date of Last Dose Date of First Dose + 1.
- Study duration will be defined as the total number of days in the study (date of last visit date of informed consent + 1).
- History of developmental regression will be determined from the medical history question as reported on the PMS diagnosis page of the CRF: "Has the child undergone a regression of skills in the past?" If coded as "yes" the subject is considered as having had a past developmental regression.
- Autism Spectrum Disorder (ASD) diagnosis will be derived from the PMS diagnosis page of the CRF. If ASD is checked to the under "confirmation of psychiatric co-morbidities", the subject is considered as having the disorder-
- Bipolar Disorder will be derived from the PMS diagnosis page on the Case Report Form (CRF). If "Bipolar disorders" is checked to the under "confirmation of psychiatric co-morbidities", the subject is considered as having the disorder.

- Attention Deficit Disorder will be derived from the PMS diagnosis page on the CRF. If "Attention Deficit Disorder" is checked to the under "confirmation of psychiatric co-morbidities", the subject is considered as having the disorder.

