- Obsessive-compulsive Disorder will be derived from the PMS diagnosis page on the CRF. If "Obsessive-compulsive disorder" is checked to the under "confirmation of psychiatric co-morbidities", the subject is considered as having the disorder.
- Dose modification is defined as dose increased, dose reduced, or dose interrupted responses for the action taken with study treatment on the adverse event (AE) CRF.
- Improvement in the top 3 concerns will be derived as a decrease in severity (change from baseline <0).
- Baseline seizure frequency will be determined based on the number of seizures recorded in the diary during the 4–6-week screening period. The baseline monthly seizure frequency will be derived by dividing the total number of seizures during the screening/baseline period by the screening/baseline duration in months ([first dose date screening date] divided by 30.4375). The baseline weekly seizure frequency will be derived by dividing the total number of seizures during the screening/baseline period by the screening/baseline duration in weeks ([first dose date screening date] divided by 7). During the treatment period (Visits 4 16), the seizure frequency will be derived by summing the number of seizures recorded in the diary over treatment. The monthly seizure frequency will be derived by dividing the total number of seizures during the treatment period by the treatment duration in months (treatment duration divided by 30.4375). The weekly seizure frequency will be derived by dividing the total number of seizures during the treatment period by the treatment duration in weeks (treatment duration ([first dose date screening date] divided by 7).
- The Mullen Scales of Early Learning developmental quotient (DQ) is calculated as the (mean of the age equivalent in months of the corresponding scales/chronological age in months) x 100. For the overall DQ, the mean of the fine motor, receptive language, expressive language, visual reception is included. For the non-verbal DQ, the mean of the fine motor and visual reception scales are included. For the verbal DQ, the receptive language and expressive language scales are included.
- For the Mullens Scales of Early Learning and the Stanford-Binet 5, Chronological age in months will be calculated as (date of assessment date of birth + 1)/30.4375.

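### SAP 6.9 compares a raw seizure count over 4 to 6 weeks with a raw count over about 91 days, so an unchanged seizure rate appears as a 2.17- to 3.25-fold rise

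*SAP*

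**What the plan says.** SAP Section 6.9 sits in the safety analysis and takes its seizure variables from Section 4.3. It plans this display: "Summary statistics on the observed and the change from baseline in total and monthly seizures will be displayed at baseline and end of treatment". The sentence after it reads: "Within subject changes will be assessed using a Wilcoxon Signed Rank Test". That sentence names no variable.

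Section 4.3 supplies the pieces:

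- Baseline count: "Baseline seizure frequency will be determined based on the number of seizures recorded in the diary during the" 4 to 6 week screening period.
- Treatment count (Visits 4 to 16): "the seizure frequency will be derived by summing the number of seizures recorded in the diary over treatment".
- Change from baseline: "will be derived as the measurement taken at the specified visit minus the baseline measurement".
- Monthly rate on treatment: "The monthly seizure frequency will be derived by dividing the total number of seizures during the treatment period by the treatment duration in months". The baseline monthly rate is likewise divided by its own duration.
- Treatment duration: "Treatment duration in days will be derived as follows: Date of Last Dose" minus the first dose date, plus one. It therefore counts dosing days.
- Weekly rate on treatment: the text divides "seizures during the treatment period by the treatment duration in weeks (treatment duration ([first dose date screening date] divided by 7". The bracket names the span from screening to first dose, which is the baseline period.

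Nothing in 4.3 or 6.9 puts the total on a common time base.

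**The concern.** The difference in totals subtracts a count over a short window from a count over a window two to three times as long. It contains the difference in observation time as well as any change in seizure frequency, and for a child with a stable rate it contains only the former. The error runs in one direction: it makes treatment look harmful and can hide a real fall. Total and monthly rows of the same display could point in opposite directions, with no rule on which to read.

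The monthly rate also needs one clarification before it carries the test alone. Its numerator is diary seizures over Visits 4 to 16 and its denominator is dosing days. Protocol Sections 7.2.2 and 9.4.5 say that stopping IMP is not necessarily withdrawal from the study, and Table 1 footnote k keeps the diary running to two weeks after the EOT visit. Section 4.3 does not say whether seizures after an early stop but before Visit 16 are counted.

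**Working it through.** **Inputs.** Baseline window: 4 to 6 weeks, or 28 to 42 days (Protocol 9.1). Treatment window: 13 weeks; 13 × 7 = 91 days, which matches the duration in Protocol 9.4.2. Month length: 30.4375 days (SAP 4.3).

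**Unchanged rate.** The ratio of totals equals treatment days divided by baseline days:

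- 91/42 = 2.17
- 91/28 = 3.25

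**Fall that would show as no change.** One minus baseline days over treatment days:

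- 1 − 42/91 = 0.54
- 1 − 28/91 = 0.69

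**Sensitivity to the windows.** If EOT falls 3 days early and counting stops at Day 88, the ratios are 88/42 = 2.10 and 88/28 = 3.14, and the hidden falls are 1 − 42/88 = 0.52 and 1 − 28/88 = 0.68. Moving the baseline limits out by 2 days gives 91/44 = 2.07 and 91/26 = 3.50.

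**Example: a child with 1 seizure per week at baseline, 91 days of treatment.**

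| Baseline | True rate on treatment | Total, baseline → treatment | Change in total | Monthly rate, baseline → treatment |
|---|---|---|---|---|
| 28 days | unchanged | 4 → 13 | +9 | 4.35 → 4.35 |
| 42 days | unchanged | 6 → 13 | +7 | 4.35 → 4.35 |
| 28 days | halved | 4 → 6.5 | +2.5 | 4.35 → 2.17 |
| 42 days | halved | 6 → 6.5 | +0.5 | 4.35 → 2.17 |

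Monthly rates: 4/(28/30.4375) = 6/(42/30.4375) = 13/(91/30.4375) = 4.35, and 6.5/(91/30.4375) = 2.17. With the rate halved, the total still rises.

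**What the test would do.** The documents give no seizure rates for this sample, so this part is illustrative. If every non-zero change is positive, the exact two-sided signed rank p-value is 2/2ⁿ: 0.0625 for n = 5, 0.031 for n = 6 and 0.0078 for n = 8. Six children with a rise are therefore enough. Protocol 5.1 puts seizures at about 40–60% of affected individuals. If that applied here it would mean 8 to 12 of 20 children, though not necessarily with seizures in the diary.

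A simulation with no true change used Poisson counts and constant individual rates drawn from a gamma distribution with an assumed mean of 1, 4 or 10 seizures per month. It took 8, 10 or 20 children with seizures and 1,000 runs per setting, and tested by the normal approximation. The test on totals declared a significant worsening in 24% to 100% of runs. The test on the monthly rate rejected in 3.6% to 6.5%.

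**Monthly rate after an early stop.** Suppose seizures are counted to Day 91 but divided by dosing days. A child stopping on Day 63 has the rate inflated by 91/63 = 1.44 (6.28 instead of 4.35 in the example). A child stopping on Day 42 has it inflated by 91/42 = 2.17 (9.42 instead of 4.35).

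**The case against.** The best defence is that the reader is not left with the total alone. The monthly change appears beside it, properly scaled, and SAP 6.1 summarises treatment duration. This limits the harm but does not justify displaying a change that is mostly window length whenever the rate is stable.

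That the total will be tested is an inference. The test sentence names no variable, and SAP 7.5 calls all significance levels nominal. But the sentence directly follows one naming total and monthly changes and excludes neither, so a programmer could reasonably test both. The displayed change would mislead even without a p-value.

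The fold range needs a child with seizures, a full course and a nominal baseline. Children with no seizures in either period contribute zero, and early discontinuation lowers the ratio. These conditions stand.

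The early-stop inflation is open to challenge. Protocol 9.4.5 and Table 1 footnote b ask children who discontinue early after Visit 5 to return for the EOT assessments. If that visit came 3 to 7 days after a Day 63 stop (an assumption), inflation would be only 66/63 = 1.05 to 70/63 = 1.11. Against this, Protocol 7.2.2, 9.4.2 and 9.4.5 also ask that scheduled evaluations continue after IMP stops. Both readings are available, so the interval needs stating; 1.44 and 2.17 apply only to the second reading.

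The weekly bracket looks like leftover text. Section 6.9 names weekly frequency but specifies no weekly display, so it matters only if weekly rates are reported.

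Finally, seizure counts are not among the efficacy variables in SAP 7.1, and DSMC decisions on up-titration and age groups use raw listings (SAP 3). That bears on severity, not on whether the rule is wrong.

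**Conclusion.** The concern holds. Followed as written, SAP 4.3 and 6.9 subtract unscaled counts from windows of 28–42 and about 91 days. With a full course, a nominal baseline and a non-zero unchanged rate, the total rises 2.17- to 3.25-fold, and a true fall of 54% to 69% disappears. How often this would give a nominally significant worsening depends on seizure rates and numbers that the documents do not provide.

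The fault is confined to the total. The monthly rate is sound for children who complete treatment and needs only a stated counting interval for those who stop early. The tests are nominal and no trial decision rests on them, so this should be fixed but does not threaten the primary objective. It is best done before database lock, because SAP Section 4 treats analyses added later as post hoc.

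**What to change.** In SAP 6.9:

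- Show total seizures by period alongside the days observed, with no change from baseline and no test.
- State that the signed rank test applies only to the time-scaled rate.
- State whether weekly rates are displayed.

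In SAP 4.3:

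- State that seizures and days are counted over the same diary interval in each period.
- Say which interval applies to a child who stops IMP early but keeps the diary: count and days both to last dose, or both to Visit 16.
- Replace the bracket in the on-treatment weekly formula with treatment duration divided by 7, using the same day count as the monthly rate.

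The cost is SAP wording and programming. The daily diary and the dosing dates are already collected, so no new data are needed.

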7.1. Efficacy Variables

There are no primary efficacy variables.

Secondary variables for efficacy to be considered include:

- PMS-specific Clinical Global Impression Scale—Overall Improvement (CGI-I)
 Score
- PMS-specific Clinical Global Impression Scale–Domain Improvement Scores
- PMS Domain Specific Rating Scale Improvement Scores
- Caregiver Impression of Change Score
- Clinical Global Impression Scale-Severity (CGI-S)-Overall Severity Score
- Clinical Global Impression Scale-Severity (CGI-S)-Domain Scores
- MacArthur-Bates Communicative Development Inventory (MB-CDI) Scores
- Observer-Reported Communication Ability (ORCA) Score
- Caregiver Top 3 Concerns Likert Scale Scores
- Aberrant Behavior Checklist-2 (ABC-2) Scores
- Behavior Problems Inventory-Short Form (BPI-SF) Scores
- Child Sleep Habits Questionnaire (CSHQ) Scores
- Gastrointestinal Health Questionnaire (GIHQ) Scores
- Vineland Adaptive Behavior Scales-3 Growth Scale Scores
- Quality of Life Inventory-Disability (QI-Disability) Scores
- Impact of Childhood Neurological Disability (ICND) Overall quality of life rating
- Stanford-Binet raw, z-deviation, age-equivalent, and Change Sensitive scores or Mullen Scales of Early Learning raw, age-equivalent and Developmental Quotient scores

Biomarker variables and gut microbiome analyses will be described in a separate analysis plan.

7.2. Adjustments for Covariates

A list of potential covariates to be used in descriptive summaries or analyses are provided below.

- Age (9-12, 6-8, 3-5 yrs)
- Sex (Male, Female)
- SB5 NVIQ or MSEL NV Developmental Quotient
- History of developmental regression (yes, no)
- ASD diagnosis (yes, no)

7.3. Examination of Subgroups

No subgroup analyses are planned.

7.4. Multicenter Studies

All sites will be pooled for this analysis.

7.5. Multiplicity Comparison/Multiplicity

No hypothesis testing is planned; therefore, there will be no adjustments for multiplicity and all reported significance levels will be nominal.

8. Efficacy Analysis Methods

8.1.1. Primary Efficacy Analysis

There is no primary efficacy endpoint.

8.1.2. Secondary Efficacy Analysis

The efficacy endpoints will be analyzed using a Wilcoxon signed rank test on the paired subject data from baseline to end of treatment (Visit 16) when applicable. Descriptive statistics will be used to summarize the data. For total scores, waterfall plots, histograms, and violin plots will also be created at the End of Treatment (EOT) visit with plots for all subjects and separate plots color-coded to indicate age group (9-12 years, 6-8 years, 3-5 years), NVIQ/DQ score (≥ 50 , < 50), sex (Male, Female) and number of concomitant medications (> 6, ≤ 6). The number of concomitant medications will be determined as defined in Section 4.3. For scales with domain scores, forest plots will be generated.

Results for each efficacy variable will also be listed by subject.

8.1.2.1. Clinical Global Impression Scale—Overall Improvement (CGI-I) Score

Clinical Global Impression of Improvement assessments are completed at Visit 9 (Week 6), End of Treatment (Week 13, Visit 16), and Follow-up (Visit 17). The clinician rates how much the subject's illness has improved or worsened relative to the baseline visit (Visit 3). The Overall CGI-I score is rated on a 7-point scale, where 1='very much improved'; 2='much improved'; 3='minimally improved'; 4='no change'; 5='minimally worse'; 6='much worse'; 7='very much worse'. Scores of 1, 2, and 3 indicate improvement. Within-subject change is indicated by the score at each relevant follow-up visit (Week 6, Visit 9 and Week 13, EOT, Visit 16). If an overall score is missing, that subject will be excluded from analysis.

Summary statistics for the CGI-I Overall score will be displayed at all post-baseline visits. Within-subject changes will be analyzed using a Wilcoxon signed rank test. Waterfall plots, histograms, and violin plots will be generated as described in Section 8.1.2.

[figure not shown]

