11.4 Efficacy Analysis

Efficacy will be assessed by looking at within-subject changes from the Baseline period to EOT using the efficacy endpoints listed in Section 6.3.2.

The subject's baseline characteristics and symptom severity will be established based on assessments collected during the 4 to 6 week Screening/Baseline period. Baseline values will be based on the average values of visits 1, 2, and 3 for assessments collected at more than one visit. A Wilcoxon signed rank test will be used to test for improvement and an exact significance level will be computed.

Potentially influential factors will be considered and addressed with a linear regression model. This model may include covariates such as age, sex, nonverbal IQ (NVIQ) or NVIQ equivalent, genotype, history of regression (yes/no), ASD diagnosis (yes/no) with no more than two covariates included in any model. Descriptive statistics and corresponding graphics will be used to present the results. The safety and efficacy analysis details will be specified in the SAP.

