4.1. Determination of Sample Size

Sample sizes were estimated for this open-label study using within-subject change as the measure of improvement. Given the limited data from interventional trials in these patient populations, and that this is the first clinical study of NNZ-2591 IMP in this population, treatment change estimates were based on Clinical Global Impression Scale of Improvement (CGI-I) data from completed clinical trials in other rare, neurodevelopmental disorders. Based on the information provided in Glaze et al. 2019 (Double-blind, randomized, placebo-controlled study of trofinetide in pediatric Rett syndrome), the standard deviation of the CGI-I is approximately 0.7 at a single timepoint. For a sample size of 20 subjects, a two-sided significance level of 0.05, and a Wilcoxon signed-rank test, the study will be able to detect a difference of 0.55 units of change in the CGI-I at a power of 0.90. For a power of 0.80, 0.85, and 0.90, the detectable difference would be 0.48, 0.51, and 0.55 or larger, respectively. The effect size for a power of 0.80, 0.85, and 0.90 is 0.68, 0.73, and 0.79, respectively. If the observed standard deviation is larger, the size of the detectable difference would also be larger. For example, if the standard deviation is 1.45, the detectable difference for a power of 0.80, 0.85, and 0.90 is 1.02, 1.09, and 1.18 or larger, respectively.

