8.1.2.2. Clinical Global Impression Scale—Domain Improvement Scores

Clinical Global Impression of Improvement assessments are completed at Visit 9 (Week 6), End of Treatment (Week 13, Visit 16), and Follow-up (Visit 17). The clinician rates

how much the subject's illness has improved or worsened relative to the baseline visit (Visit 3) in each domain. The seven domain improvement scores are: expressive communication, receptive communication, gross motor function, fine motor function, social interaction, self-care, and cognition/learning. The individual domain CGI-I scores are rated on a 7-point scale, where 1='very much improved'; 2='much improved'; 3='minimally improved'; 4='no change'; 5='minimally worse'; 6='much worse'; 7='very much worse'. Scores of 1, 2, and 3 indicate improvement.

Within subject change is indicated by the score at each relevant follow-up visit (Week 6, Visit 9 and Week 13, EOT, Visit 16). If a domain score is missing, that subject will be excluded from analysis for that domain. Domain scores will be presented in forest plots, as described in Section 8.1.2.

Domain scores as reported on the CRF will be summarized at each post-baseline visit, in the same manner as the CGI-I Overall Score.

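### Does the CGI-I signed-rank test lose its meaning because the SAP never names 4 as the reference value?

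*SAP*

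**What the plan says.** SAP 4.3 sets the CGI-I apart from the other scales: "CGI-I will not have a change from baseline measurement; the within-subject treatment change is assessed by the value at the End of Treatment Visit". SAP 8.1.2.1 repeats the idea for each follow-up rating ("Within-subject change is indicated by the score at each relevant follow-up visit") and then states: "Within-subject changes will be analyzed using a Wilcoxon signed rank test". The same section lists the seven anchors, with 4 meaning no change, and says that scores of 1, 2 and 3 count as improvement relative to Visit 3.

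The general rule in SAP 8.1.2 applies the signed-rank test "on the paired subject data from baseline to end of treatment (Visit 16) when applicable". For the seven domains, SAP 8.1.2.2 says: "Domain scores as reported on the CRF will be summarized at each post-baseline visit, in the same manner as the CGI-I Overall Score".

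The purpose and scale of the test are given elsewhere. Protocol 11.4: "A Wilcoxon signed rank test will be used to test for improvement and an exact significance level will be computed". SAP 4.1, for 20 subjects and an SD of about 0.7: "the study will be able to detect a difference of 0.55 units of change in the CGI-I at a power of 0.90". On the standing of the results, SAP 7.5 plans no hypothesis testing and adds that "all reported significance levels will be nominal"; SAP 8.1.1 says there is no primary efficacy endpoint.

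**The concern.** A one-sample signed-rank test needs a reference value. For scales analysed as a difference from baseline, zero is the natural one. The CGI-I is first rated at Week 6, so it has no baseline rating to pair with, and the change is defined as the raw score. If a programmer reused the code written for change scores, the test would ask whether numbers between 1 and 7 exceed zero. The answer is always yes, so the p-value would reflect only how many children were rated and could not separate improvement from no change or worsening.

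The CGI-I is also the endpoint on which the sample size rests. If the domains were tested in the same way, eight p-values at end of treatment (one overall plus seven domains) would be uninformative.

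**Working it through.** **Inputs.** From SAP 4.1: n = 20, SD 0.7, two-sided 0.05, detectable differences 0.48, 0.51 and 0.55 at power 0.80, 0.85 and 0.90, effect sizes 0.68, 0.73 and 0.79. From SAP 8.1.2.1: scores 1 to 7, with 4 as no change. The rating sets below are assumed, for illustration only.

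**1. Reproduce the plan's sizing.** Use one-sample noncentral-t power with the signed-rank efficiency under normality, so effective n = 20 × 3/π ≈ 19.1.

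| Power | Effect size, computed (stated) | × 0.7, computed (stated) |
|---|---|---|
| 0.80 | 0.678 (0.68) | 0.474 (0.48) |
| 0.85 | 0.725 (0.73) | 0.507 (0.51) |
| 0.90 | 0.784 (0.79) | 0.549 (0.55) |

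At a difference of 0.55 the power is 0.901 by formula and 0.902 by simulating the exact signed-rank test. The plan's figures hold.

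**2. What reference do those figures imply?** The ratio 0.55/0.7 = 0.79 does not settle it, because it is the same for any reference. The scale does: the lowest possible score is 1, so no mean score can lie 0.55 from zero. Measured from 4, an improvement of 0.55 is a mean of 4 − 0.55 = 3.45, an ordinary result.

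**3. The literal reading against zero.** All n differences are positive, so the exact two-sided p is 2/2^n:

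- n = 5: 0.0625
- n = 6: 0.031
- n = 15: 6.1e-5
- n = 20: 1.9e-6

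From six rated children upward it is always below 0.05.

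**4. The two readings side by side, n = 20** (zeros dropped, mid-ranks for ties).

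| Ratings | Mean | p against 0 | p against 4 |
|---|---|---|---|
| twenty 4s | 4.00 | 1.9e-6 | 1.0 |
| six 3s, eight 4s, six 5s | 4.00 | 1.9e-6 | 1.0 |
| thirteen 3s, five 4s, two 5s | 3.45 | 1.9e-6 | 242/32768 = 0.0074 |
| fourteen 5s, six 4s | 4.70 | 1.9e-6 | 0.00012 |

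In the third row 15 ratings differ from 4, all by one unit, so the count is 2 × (1 + 15 + 105) = 242 out of 2^15 = 32768. Under an assumed symmetric no-effect distribution with SD 0.77, the test rejects in 2.1% of samples against 4 and in all samples against zero.

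**5. Does the text send anyone to zero?** No passage gives zero as the null for the CGI-I. The anchors, the definition of improvement, the sizing and the protocol's stated purpose all point to 4. SAP section 1 says the SAP is to be read together with the protocol, and on this point the two do not conflict. SAP section 4 has every program checked by an independent programmer, including whether the method is statistically valid. A test that gives the same p-value for all 1s and all 7s would not pass that check.

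**6. Related points.**

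- *Domains.* SAP 8.1.2.2 says they are summarised like the overall score and names no test. A domain test is an inference from that sentence or from the general rule in 8.1.2.
- *Early stoppers.* Footnote b to SAP Table 1 brings children who stop after Visit 5 back for the assessments scheduled at Visit 16, and SAP 4.2.3 analyses discontinued subjects up to their last observation. Using that rating as the end-of-treatment value is already implied.
- *Caregiver Impression of Change.* SAP 8.1.2.4 invokes LOCF for a scale completed only at Visit 16. There is no earlier value to carry, so the sentence has no effect on any result.

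**The case for a change.** The strongest case for acting is that the SAP governs where the documents differ, that analyses added after database lock are labelled post hoc, and that one sentence naming 4 would cost almost nothing. The general rule in 8.1.2 cannot supply the reference, because there is no baseline rating. For the endpoint behind the sample size, a reader might reasonably want the null in writing.

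Much of this is true: no visible sentence says that 4 is subtracted, and the arithmetic against zero is correct. It does not follow that the planned analysis is wrong or open to choice. The test itself is pre-specified, and only one reference value makes sense of the anchors, the sizing and the protocol's purpose. Using 4 carries out the plan and is not an addition after lock. The harm also depends on a reading that the text never states and that independent validation should catch. What stands is a drafting omission.

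**Conclusion.** No change to the plan is needed. The reference value for the overall CGI-I is unstated but recoverable: it is 4, and the plan's own power figures reproduce (0.901 against a stated 0.90) on a difference that can only be measured from there.

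The literal alternative would be worthless, with p = 1.9e-6 at n = 20 whatever the ratings, but nothing in the SAP prescribes it. If it were run by mistake, the summary statistics, histograms, waterfall plots and by-subject listings would show the actual ratings beside it. No formal decision rests on the p-value, since efficacy is secondary and significance levels are nominal.

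This conclusion assumes that the analyst reads the anchors in 8.1.2.1 together with 4.1 and Protocol 11.4, and that the validation described in SAP section 4 is carried out. The related points on domains, early stoppers and LOCF alter no planned result.
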